Study Protocol and Statistical Analysis Plan

Official Title: Metacognitive Therapy and Intolerance-of-Uncertainty Therapy for Generalized Anxiety Disorder in Primary Care: Randomized Controlled Pilot Study

NCT Number: NCT03621371

Document Date: 4 July 2024

Study Protocol

Objective. Feasibility and preliminary efficacy of two psychological treatments based on cognitive-behavioral therapy – metacognitive therapy (MCT) and intolerance-of-uncertainty therapy (IUT) – for primary care patients with a principal diagnosis of generalized anxiety disorder in Stockholm, Sweden are investigated in a pilot study using a randomized controlled trial design. The purpose of the study is to examine the feasibility of a full-scale randomized controlled trial. Design. Randomized controlled pilot trial. Methods. Research questions primarily concern recruitment, assessment, and therapist competence and adherence. Secondary research questions concern treatment efficacy. Primary treatment outcome measure is total scores on the Penn State Worry Questionnaire (PSWQ).

Statistical Analysis Plan

Statistical analyses are performed using the SPSS (Version 27, SPSS Inc., Chicago, IL). Proportions, means, and standard deviations (SDs) are calculated for feasibility measures. Differences in session attendance between the IUT and MCT conditions are investigated using an independent t-test and differences in dropout with a Fisher's exact test. In the preliminary evaluation of treatment effects, multilevel modeling is used to estimate the effects of time and of time by condition on continuous outcome measures from the pre-treatment to the post-treatment assessment and from the post-treatment to the follow-up assessment. The maximum likelihood method is used to estimate model parameters. Different covariance structures are tested. Models are built in a stepwise fashion, starting with a basic model with a fixed intercept, then adding random parameters (intercept and slope), and finally adding a time by group interaction term to the model. Each model's fit to observed data is evaluated with the likelihood ratio test. Models with significantly better fit than previous models are retained. Standardized effect sizes for between-group effects at mid-treatment, post-treatment,

and follow-up are calculated as Cohen's d for multilevel models, using the SD for the pooled sample at pre-treatment and the pooled sample SD at post-treatment (for post-treatment to follow-up). For between-group effect size estimations, the beta coefficient (difference in change trajectories between treatments) is multiplied by treatment duration at mid-treatment, the average treatment duration, or the follow-up duration, and then divided by the pooled SD of observed values at pre-treatment or post-treatment. For model-based d , 95% confidence intervals are calculated. In keeping with the principle of intention-to-treat, data from all participants are used in the multilevel models.

Treatment response is assessed with the reliable change index (RCI), which is calculated using the internal consistency reliability of the PSWQ and the sample SD of this measure at pre-treatment. An RCI of $z \geq -1.96$ indicates reliable improvement, whereas an RCI of $z \geq 1.96$ indicates reliable deterioration. Differences in improvement and deterioration between conditions at the post-treatment and follow-up assessment are investigated with chi-square tests or Fisher's exact tests.

To assess recovery rates, two procedures are employed that combine statistically reliable change with clinically meaningful change. First, an RCI of 7 points and a cut-off of 53 points on the PSWQ as used in a previous study are applied. Second, the same RCI and a cut-off of 47 points as used in another previous study are applied. Differences in recovery rates between groups at post-treatment and follow-up assessment are investigated with chi-square tests or Fisher's exact tests.

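### Post-treatment to follow-up model is under-specified: fitted separately with only time and time by condition, its interaction would generally not be the difference in change if the arms differ at post-treatment

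*Combined protocol and SAP*

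**What the plan says.** The Statistical Analysis Plan section states that "multilevel modeling is used to estimate the effects of time and of time by condition on continuous outcome measures", and that this is done "from the pre-treatment to the post-treatment assessment and from the post-treatment to the follow-up assessment". The models are built in steps from a fixed intercept, "then adding random parameters (intercept and slope), and finally adding a time by group interaction term to the model". No step adds a condition effect. No step adds a fixed time effect either, although time is one of the effects to be estimated.

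For the between-group effect sizes, the plan explains the coefficient and its first multiplier thus: "the beta coefficient (difference in change trajectories between treatments) is multiplied by treatment duration at mid-treatment". Later time points take multipliers of their own, and the sentence ends: "or the follow-up duration, and then divided by the pooled SD of observed values at pre-treatment or post-treatment". The second interval therefore has its own multiplier (follow-up duration) and its own standardizer (post-treatment SD). The plan also states: "In keeping with the principle of intention-to-treat, data from all participants are used in the multilevel models".

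It does not say whether post-treatment to follow-up is a separate fit or a segment of one model, where time zero lies, or whether the list of terms is complete.

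**The concern.** Leaving out a condition main effect is defensible from pre-treatment to post-treatment, because randomisation makes the expected starting difference zero. It is not defensible on that ground from post-treatment onward, since a difference at post-treatment is what a comparison of two treatments looks for. A separate model without a condition term gives both arms the same expected value at time zero. If time zero is post-treatment, part of any existing gap is moved into the interaction.

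That coefficient feeds the follow-up Cohen's d and its confidence interval. A gap that is merely maintained would look partly like further divergence, and a gap that shrinks could look stable. Whether a difference is maintained, grows or fades is the question this interval is there to answer.

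**Working it through.** **Inputs.** From the plan: the named terms (time, time by condition), maximum likelihood estimation, retention of terms by likelihood ratio test, and the meaning given to beta. Assumed, because the documents give no sample size, SD, correlation, expected difference or test level: two occasions with complete data, variance 1 at each, correlation rho, and a 0.05 test. D_post and D_FU are the true arm differences in SD units. The plan has no figure of its own to reproduce.

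**Formula.** Without a condition term, the interaction is x'V⁻¹d / x'V⁻¹x, where d = (D_post, D_FU) and x holds the time codes. With time zero at post-treatment, x = (0, 1), this becomes

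interaction = D_FU − rho × D_post.

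The difference in change is D_FU − D_post, so the distortion is (1 − rho) × D_post. With unequal variances, rho is replaced by the slope b = cov(post, follow-up)/var(post). With the condition term, the two-occasion mean model is saturated and the interaction is D_FU − D_post exactly.

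**Maintained gap (true difference in change 0), time zero at post-treatment.**

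| D_post | rho 0.5 | rho 0.6 | rho 0.7 | rho 0.9 |
|---|---|---|---|---|
| 0 | 0 | 0 | 0 | 0 |
| 0.2 | 0.10 | 0.08 | 0.06 | 0.02 |
| 0.5 | 0.25 | 0.20 | 0.15 | 0.05 |

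**Shrinking gap, rho 0.5 / 0.6 / 0.7.**
- 0.2 to 0.1 (true −0.10): 0.1 − rho × 0.2 = 0.00 / −0.02 / −0.04.
- 0.5 to 0.3 (true −0.20): 0.3 − rho × 0.5 = +0.05 / 0.00 / −0.05.

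**Time coded from pre-treatment.** Now x = (t_post, t_FU) and the effect is beta × (t_FU − t_post). For a maintained gap D, with x = (3, 6) and rho 0.5: beta = D × 0.5 × 9 / (9 + 36 − 18) = D/6, and multiplying by 3 gives 0.5 × D. Over x = (3, 6), (3, 9) and (3, 15) and rho 0.5 to 0.7, the result is 0.08 to 0.11 SD for D = 0.2 and 0.19 to 0.29 SD for D = 0.5. This coding does not rescue a maintained gap.

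**Exceptions.** The distortion is zero if b is exactly 1 (and changes sign if b exceeds 1). It is also zero, with time coded from pre-treatment, if the gap grows in proportion to time: x = (3, 6) with a gap going from 0.2 to 0.4 gives exactly 0.20, for any rho.

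**Likelihood ratio retention.** Maintained gap, rho 0.6, unstructured covariance, time zero at post-treatment, 6,000 simulated trials per cell, at 20 / 30 / 50 per arm:
- gap 0: 6.2 / 5.2 / 5.0%
- gap 0.2 SD: 7.3 / 7.0 / 8.4%
- gap 0.5 SD: 13.5 / 15.6 / 22.7%
- with the condition term: 5.1 to 6.2% throughout.

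**Price of the condition term.** At rho 0.6 with n per arm and known covariance, the interaction variance is 2(1 − rho²)/n = 1.28/n without the term and 4(1 − rho)/n = 1.6/n with it. Mean squared error without the term adds the squared distortion.

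| Gap | n = 20, without / with | n = 30, without / with | n = 50, without / with |
|---|---|---|---|
| 0.2 (0.08² = 0.0064) | 0.070 / 0.080 | 0.049 / 0.053 | 0.032 / 0.032 |
| 0.5 (0.20² = 0.04) | 0.104 / 0.080 | 0.083 / 0.053 | 0.066 / 0.032 |

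**The case against.** The strongest reply is that the documents do not establish the harmful model. A piecewise model with a duration and a standardizer for each segment fits the wording as well as a separate fit does. The build steps also leave out fixed time, which is certainly meant to be in the model, so silence about condition is weak evidence that it is excluded. The plan's own gloss on beta as a difference between the arms in change suggests a model that delivers that quantity. A reader might infer that the plan definitely omits the condition effect, or that the follow-up effect size is biased. The text supports neither. This part of the objection stands, and it makes the point conditional.

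Three further replies stand in part:
- D_FU − rho × D_post is not meaningless. It is in effect the follow-up difference adjusted for the post-treatment score. It is still not the quantity the plan names.
- At a 0.2 SD gap with 20 to 50 per arm, adding the condition term does not lower total error. The case for it there is that the estimate means what the plan says it means, not that it is more accurate overall. At 0.5 SD total error does fall, but nothing in the documents projects a gap of that size between two active treatments.
- Efficacy is a secondary question in a feasibility pilot, and the response and recovery comparisons do not use this coefficient.

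What the objection does not remove is that two analysts following this text could fit models with different estimands and report different follow-up effect sizes.

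**Conclusion.** The point holds as a conditional one. If post-treatment to follow-up is fitted separately with only time and time by condition, the interaction is generally not the difference in change when the arms differ at post-treatment. The exceptions are a follow-up-on-post-treatment slope of exactly 1 and, with time coded from pre-treatment, a gap growing in proportion to time. There is no systematic distortion if the arms are truly equal at post-treatment.

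The size rests entirely on assumed gaps and correlations. At the smaller assumed gap the effect on retention of the interaction is slight. It would be wrong to extend the point to the pre-treatment to post-treatment model, where randomisation supports a common starting mean, or to the feasibility results. Only the secondary, preliminary follow-up effect size and its interval are exposed. Priority is low, and confidence that the harmful model is the intended one is no more than medium.

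The intention-to-treat sentence is a minor wording matter: in a separate fit, a participant with neither a post-treatment nor a follow-up score would contribute nothing. The issue does not arise in a piecewise model for anyone with an earlier score.

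**What to change.** State whether the second interval is a separate fit or a segment of one model, list every fixed effect, and give the time coding. Then do one of the following:

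- keep a separate post-treatment to follow-up model and include the condition main effect; or
- fit one piecewise model over all assessments, with a knot at post-treatment and a time-by-condition term for each segment, and take the follow-up contrast from the second segment.

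Both keep the plan's effect size as coefficient times duration over SD. If a separate fit is kept, limit the sentence about using all participants, for that fit, to those with at least one of the two scores. If the sponsor already fits one of these models, a sentence saying so settles the matter.

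The cost is a few lines of plan text and a small syntax change, with no new data. The separate fit gains one parameter and a less precise interaction (variance 1.6/n against 1.28/n at rho 0.6, a ratio of 1.25), so total error is not reduced when the post-treatment gap is small. The piecewise option is a slightly larger model.

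### Maximum likelihood with no REML refit or small-sample degrees of freedom is likely to make the 95% CI for the between-group d somewhat too narrow in a small pilot, if patients' slopes vary

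*Combined protocol and SAP*

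**What the plan says.** The point concerns the multilevel-model and effect-size text under the heading Statistical Analysis Plan.

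- Estimation: "The maximum likelihood method is used to estimate model parameters". No other estimation method is named.
- Model building starts from a fixed-intercept model, "then adding random parameters (intercept and slope), and finally adding a time by group interaction term to the model".
- Choice between steps: each model's "fit to observed data is evaluated with the likelihood ratio test", and "Models with significantly better fit than previous models are retained". The significance level is not given.
- Covariance: "Different covariance structures are tested". Neither candidates nor criterion are listed.
- Segments: effects are modelled "from the pre-treatment to the post-treatment assessment and from the post-treatment to the follow-up assessment".
- Effect size: the slope difference is multiplied by a duration "and then divided by the pooled SD of observed values at pre-treatment or post-treatment". For the resulting d, "95% confidence intervals are calculated".

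The document does not give the sample size, the number of measurements per segment, the expected variation in slopes, the method for the CI, or the degrees of freedom. A mid-treatment effect size is planned, which suggests but does not establish that the treatment phase has at least three measurements.

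**The concern.** ML is the right choice for likelihood ratio tests that compare fixed effects. It is less suitable for the reported standard errors, because it estimates variances without allowing for the fixed effects already fitted and so understates them in small samples. The numerator of d is the slope difference, so its interval inherits that understatement.

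A second effect may add to the first. If the random slope has to earn its place by a significance test of its own, a small trial will often fail to detect slope variation that is real. The model then treats differences in patients' rates of change as measurement noise, and the standard error of the slope difference is again too small.

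At stake is how uncertain the trial says it is about the difference between MCT and IUT. The time-by-condition test would be somewhat liberal for the same reasons.

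**Working it through.** The plan has no figure to reproduce. Every sample size, occasion count and variance below is an assumption.

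**1. ML alone, random slope kept.** Take balanced, complete data with two arms and total N, and a fitted slope variance above zero. The estimated slope difference is then the difference between the arms' mean individual least-squares slopes. REML divides the pooled sum of squares of those slopes by N − 2 and ML divides it by N, so

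SE(ML) / SE(REML) = √((N − 2)/N).

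The estimate's error divided by SE(REML) follows t on N − 2 df. An interval of ± q × SE(ML) therefore covers with probability 2·F(q·√((N − 2)/N)) − 1, where F is the t distribution function on N − 2 df. The plan does not state q, so two values are shown: 1.96, and the 97.5% point of t on N df.

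Example, N = 20: √(18/20) = 0.949, so the SE is 5.1% too small. With q = 1.96 the effective multiplier is 1.96 × 0.949 = 1.86, which on 18 df covers 92.1%.

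| Total N | SE ratio | SE too small by | Coverage, 1.96 | Coverage, t on N df |
|---|---|---|---|---|
| 20 | 0.949 | 5.1% | 92.1% | 93.7% |
| 32 | 0.968 | 3.2% | 93.3% | 94.2% |
| 40 | 0.975 | 2.5% | 93.6% | 94.4% |
| 64 | 0.984 | 1.6% | 94.2% | 94.6% |
| 100 | 0.990 | 1.0% | 94.5% | 94.8% |

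**2. ML plus a separate test of the random slope.** Simulation, 2,000 runs per scenario (Monte Carlo error about 0.5 points): linear change; 10, 16 or 32 per arm; 3, 6 or 12 occasions; random-intercept SD 8; residual SD 5; SD of slopes over treatment 0, 5 or 8. The slope was kept only if a 2-df likelihood ratio test against random intercept alone was significant at 0.05 (assumed). The interaction was then added and the model fitted by ML. Data were complete, a group main effect was included, and the SD in d was treated as fixed.

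Results where slopes truly vary (SD 5 or 8), as ranges over scenarios:

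| Per arm | Coverage, t | Coverage, 1.96 | Mean CI width relative to REML with slope kept |
|---|---|---|---|
| 10 | 91.4–94.1% | 90.7–92.9% | 0.85–0.94 |
| 16 | 92.1–94.4% | 91.5–93.4% | 0.90–0.97 |
| 32 | 93.0–95.2% | 92.8–94.8% | 0.95–0.98 |

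These figures contain both effects. The worst t-based case (10 per arm, 6 occasions, slope SD 5) splits as follows: ML with the slope always kept covers 94.5%, and ML after selection covers 91.4%, so selection costs 94.5 − 91.4 = 3.1 points there.

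At slope SD 5, the test kept the slope in 16%, 20% and 42% of runs (10, 16, 32 per arm) with 3 occasions, and in 59%, 80% and 98% with 12. In the runs at that SD where it was dropped, coverage was 89–93%.

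With no true slope variation, selection plus ML covered 94.4–95.7% (t), which is close to nominal.

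**3. ML with a joint step.** Random intercept and slope were tested together against a model with neither: 3 occasions, 20 or 30 per arm, residual SD 0.6 and slope SD 0, 0.5 or 0.9 of the between-person SD, 500 runs per cell (Monte Carlo error about 1 point). The random parameters were kept in 100% of runs, because the intercept variance dominates the test. ML coverage with 1.96 was 93.6–96.0%.

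**4. The remedy.** With the slope always kept, REML and t on N − 2 df, coverage in the scenarios of step 2 was 94.0–96.2% when slopes vary and 95.5–97.8% when they do not. With REML but the separate slope test left in place, it was 92.1–95.4% when slopes vary. REML alone is therefore not a complete remedy if the slope is tested on its own.

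**The case against.** The strongest reply is that the plan's wording lists random intercept and slope as a single addition. Read literally, they are tested together, the slope is practically never dropped, and only the ML effect of step 1 remains. At N = 40 to 64 that effect is an SE 1.6–2.5% too small. This stands: the text does not exclude entering the two terms one at a time, but it does not say so either, and the loss from selection must be stated as conditional.

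Other points that stand:

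- A tested residual covariance structure could absorb part of an omitted slope. The simulations did not model this.
- If post-treatment to follow-up has only two occasions, a random slope cannot be separated from residual error there, and only the ML effect applies.
- The calculations assume complete data, whereas the plan provides for dropout.
- Silence about a REML refit does not prove that none would be done.

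A reader might infer two stronger conclusions: that the intervals simply are too narrow at this trial's size, and that the full-scale trial would rest on them. The documents support neither. The first needs a sample size, an occasion count, a slope variance and a CI method, none of which is given. On the second, the protocol makes recruitment, assessment and therapist competence and adherence the main questions. Efficacy is secondary, and nothing says that d or its interval feeds the design of a later trial.

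The objection does not remove the basic point. The method as written understates the standard error in small samples when slopes vary, and a better one costs almost nothing.

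**Conclusion.** The concern holds in a limited, conditional form and is minor. If slopes vary and the random slope is kept, ML makes the SE of the slope difference 1.6% too small at a total N of 64 and 5.1% too small at 20. Coverage is then 94.6% to 93.7% with t quantiles, or 94.2% to 92.1% with 1.96.

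If the slope is also selected by its own test, total coverage at 10 per arm could fall to 91.4% (t) or 90.7% (1.96), which is 3.6 or 4.3 points below 95%. At 32 per arm the total shortfall is at most about 2 points. With a joint step there is no further loss from selection, and with no true variation in slopes coverage is near nominal.

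The direction is well supported. The size rests on assumed sample sizes, occasions and variances, on complete balanced data, and on an assumed CI method.

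**What to change.** 1. Keep ML for likelihood ratio tests of fixed effects. Refit the final model by REML, with Satterthwaite or Kenward-Roger degrees of freedom, for all reported estimates, d values and CIs, and state how the CI for d is formed.
2. For the treatment phase, if there are at least three occasions, prespecify a random intercept and random slope and do not choose them by p-value. Name a random-intercept model as the fallback if the fit does not converge, and report when it is used.
3. State the number of measurements in each segment, so that it is clear where a random slope can be estimated.

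The cost is a few sentences in the SAP and one refit per outcome. Intervals become slightly wider, and slightly conservative if slopes do not truly vary (95.5–97.8% coverage in the scenarios above).

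### The stepwise retention rule can drop the time-by-group term from which every planned between-group effect size is calculated

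*Combined protocol and SAP*

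**What the plan says.** All the relevant text is in the Statistical Analysis Plan section of the combined document.

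- **Aim of the models:** "multilevel modeling is used to estimate the effects of time and of time by condition on continuous outcome measures", over two phases (pre- to post-treatment, and post-treatment to follow-up).
- **Model building:** one stepwise sequence that begins with a fixed intercept, adds a random intercept and slope, and ends by "finally adding a time by group interaction term to the model".
- **Criterion:** each model's "fit to observed data is evaluated with the likelihood ratio test", followed by "Models with significantly better fit than previous models are retained". No step is exempted.
- **Outputs:** "Standardized effect sizes for between-group effects at mid-treatment, post-treatment" and follow-up are planned. For each, "the beta coefficient (difference in change trajectories between treatments) is multiplied by treatment duration at mid-treatment, the average treatment duration" or the follow-up duration, and the product is divided by a pooled SD. For the model-based d, "95% confidence intervals are calculated".

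Neither the aim nor the outputs are made conditional on the likelihood ratio test.

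**The concern.** The time-by-group coefficient is the randomised comparison for the continuous outcomes, including total PSWQ score, the primary treatment outcome measure. It exists only in the last model of the sequence. Applied in its ordinary sense, the retention rule discards that model when the likelihood ratio test is not significant, and the between-group d then has no source. The plan does not say which model supplies the coefficient in that case.

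Two competent analysts could therefore produce different reports from the same data. If the rule governs reporting, the d values that appear have been selected for significance. They are then too large on average, and when the true effect is small their nominal 95% intervals cover it less than 95% of the time. A full-scale trial sized on such a d could be too small. The documents do not state that use, but they do give examining the feasibility of a full-scale trial as the purpose of the study.

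**Working it through.** **1. The text.** There is no stated figure to reproduce, so the first check is a reading.

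| Case at the last step | Does the retained model contain the interaction? | Source of the between-group d |
|---|---|---|
| Likelihood ratio test significant | Yes | Its coefficient |
| Not significant | No | None stated |

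The aim and the output list require a coefficient in both rows; the rule supplies one only in the first. The second row is not rare. With no true difference it occurs in 95% of analyses at alpha 0.05, whatever the sample size.

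**2. Size of the selection effect if the rule governs reporting (illustration).** The documents give no sample size, alpha, target effect or pre-post correlation. Assumed: two-sided alpha 0.05 (z = 1.96), equal arms of n = 20, 30 or 40, correlation r = 0.5 (so the SD of change equals the baseline SD), complete data, and the pre-to-post d.

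- Standard error of d: SE = √(2(1 − r) × 2/n), which gives 0.316, 0.258 and 0.224 for n = 20, 30 and 40.
- With m = d/SE, the probability of retention is P = Φ(m − z) + Φ(−m − z).
- The mean estimate given retention is d + SE × [φ(z − m) − φ(z + m)]/P.

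One cell in full, d = 0.5 and n = 20: m = 0.5/0.316 = 1.581. P = Φ(−0.379) + Φ(−3.541) = 0.3524 + 0.0002 = 0.353. Mean = 0.5 + 0.316 × (0.3713 − 0.0008)/0.353 = 0.832, and 0.832/0.5 = 1.66.

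All cells, in the order n = 20 / 30 / 40 (coverage by simulation, 2 million draws per cell):

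| True d | Retained | Mean retained d | Ratio to truth | Coverage of the 95% CI, given retention |
|---|---|---|---|---|
| 0.2 | 0.097 / 0.121 / 0.145 | 0.694 / 0.601 / 0.537 | 3.5 / 3.0 / 2.7 | 0.693 / 0.767 / 0.813 |
| 0.3 | 0.158 / 0.213 / 0.269 | 0.768 / 0.647 / 0.573 | 2.6 / 2.2 / 1.9 | 0.830 / 0.878 / 0.905 |
| 0.5 | 0.353 / 0.491 / 0.609 | 0.832 / 0.710 / 0.641 | 1.7 / 1.4 / 1.3 | 0.928 / 0.949 / 0.959 |
| 0.8 | 0.716 / 0.873 / 0.947 | 0.950 / 0.862 / 0.825 | 1.19 / 1.08 / 1.03 | 0.965 / 0.971 / 0.974 |

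**3. Sensitivity.** Ranges of the ratio over n = 20 to 40:

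| True d | r from 0.3 to 0.7, alpha 0.05 | r = 0.5, alpha 0.10 |
|---|---|---|
| 0.2 | 2.2–3.8 | 2.4–3.0 |
| 0.3 | 1.5–2.9 | 1.7–2.3 |
| 0.5 | 1.1–1.9 | 1.2–1.5 |
| 0.8 | 1.0–1.3 | 1.02–1.13 |

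Replacing the z-test by a maximum-likelihood ratio test on two-wave change, 2n·log(1 + t²/(2n − 2)) against 3.84, gives nearly the same results. At d = 0.2 the term is retained in 0.106 to 0.150 of trials, with mean retained d from 0.662 (n = 20) to 0.529 (n = 40). At d = 0.5 the figures are 0.363 to 0.611, and 0.818 to 0.638.

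**4. Other time points.** The mid-treatment d is the same coefficient times a shorter duration, so its ratio to the truth is the same and only its absolute value is smaller. The follow-up d comes from the second phase and uses the post-treatment SD. It is subject to the same rule but was not calculated here.

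**The case against.** The strongest reply is that the section can be read without conflict. It says that models with better fit are retained; it does not say that only these are reported. The statements that time by condition is estimated and that d and its interval are calculated carry no condition, so they may be the answer: fit the interaction model, use the likelihood ratio test to judge it, and report d regardless. The list of steps is also plainly abbreviated. It names no step for a fixed effect of time, although that effect is to be estimated, so it should not be read as a complete algorithm.

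This reading is possible and may be what the authors meant. If it is followed, the rule causes no inflation. But the document does not state it, and selecting by fit is the ordinary meaning of a retention rule. A general rule that has to be set aside to obtain the promised outputs needs a sentence saying so.

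Three further points stand and limit the concern. The efficacy questions are secondary in a feasibility pilot. The illustration rests on assumed inputs and on a simpler model than the planned random-slope model. And at a true d of 0.5 or more, coverage is close to or above the nominal level (93% or higher).

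**Conclusion.** The concern holds. A stated selection rule conflicts with a stated output whenever the interaction is not significant, and the plan does not resolve that case. This conclusion rests on the text alone.

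The bias is conditional: it arises only if the rule decides what is reported. Under the assumptions in the check (20 to 40 per arm, alpha 0.05, r = 0.5) it is large for small effects and nearly vanishes at a true d of 0.8 with 40 per arm.

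The affected results are the between-group effects on the continuous outcomes. The reliable-change and recovery comparisons on the PSWQ do not use this coefficient and are unaffected. The point should be corrected, but it does not touch the primary feasibility questions.

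**What to change.** Add to the Statistical Analysis Plan: *The model containing time by condition is fitted for every continuous outcome, for the pre-to-post phase and for the post-to-follow-up phase. Its coefficient, d and 95% confidence interval are reported whatever the likelihood ratio test shows.*

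That statement alone closes the gap. It is also sound practice to confine likelihood-ratio selection to the random-effect and covariance structure, chosen with the prespecified fixed effects already in the model, and to use the test of the interaction only for its p-value. Whether the model has a condition main effect or assumes a common baseline should be prespecified too, but this correction does not depend on that choice.

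The cost is a change of wording and the reporting of some non-significant estimates with wide intervals. No new data are needed.

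### The between-group d given for follow-up measures only change after post-treatment; no continuous MCT–IUT effect from pre-treatment to follow-up is planned.

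*Combined protocol and SAP*

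**What the plan says.** The multilevel models in the Statistical Analysis Plan are to "estimate the effects of time and of time by condition on continuous outcome measures" over two consecutive windows: "from the pre-treatment to the post-treatment assessment and from the post-treatment to the follow-up assessment". No window or contrast runs from pre-treatment to follow-up.

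The effect-size text begins "Standardized effect sizes for between-group effects at mid-treatment, post-treatment" and adds follow-up as the third time point. It names two denominators, "using the SD for the pooled sample at pre-treatment and the pooled sample SD at post-treatment (for post-treatment to follow-up"). The numerator is the slope difference between treatments multiplied by a duration: time to mid-treatment, average treatment time, "or the follow-up duration, and then divided by the pooled SD of observed values at pre-treatment or post-treatment". That sentence alone does not pair durations with SDs. The pairing comes from the sentence before it and from the two modelled windows.

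Two other sets of between-group comparisons reach follow-up. For response: "Differences in improvement and deterioration between conditions at the post-treatment and follow-up assessment are investigated with chi-square tests" or Fisher's exact tests. For recovery: "Differences in recovery rates between groups at post-treatment and follow-up assessment are investigated with chi-square tests" or Fisher's exact tests. Both sets are binary and use the PSWQ only.

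The Study Protocol limits the weight of all this: "Secondary research questions concern treatment efficacy".

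**The concern.** The mid- and post-treatment d values accumulate from pre-treatment. The follow-up d starts again from zero at post-treatment and uses a different SD. Listed in one row under one description, the third value will be read as the MCT–IUT difference that remains at follow-up, and it is not that difference. A value near 0 could be taken as no difference at follow-up when an advantage has in fact lasted. A negative value could be taken as favouring the other treatment when the first is still ahead.

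As written, the plan gives no estimate with a confidence interval of the difference at follow-up for any continuous outcome. For the PSWQ, binary comparisons cover part of the gap. The other continuous outcomes have no between-group comparison of follow-up status at all. A pilot meant to inform a full-scale trial would reasonably be expected to supply that estimate.

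**Working it through.** The documents give no SDs, differences, correlations, durations or sample size, so there is no planned figure to reproduce. The algebra follows from the text; **every number below is an assumption or is computed from one**.

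**1. Algebra.** Let b1 and b2 be the slope differences in the two segments and T1 and T2 their lengths. Let D be the between-condition difference in change from pre-treatment, positive for the leading arm. Then D_post = b1·T1 and D_FU = b1·T1 + b2·T2.

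- Planned follow-up d = b2·T2 / SD_post = (D_FU − D_post) / SD_post
- From-baseline follow-up d = D_FU / SD_pre

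The planned d contains no b1 term.

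**2. Expected values.** PSWQ points, SD_pre 6 to 10, SD_post 8 to 12.

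| Case | D_post | D_FU | From-baseline d | Planned d |
|---|---|---|---|---|
| (a) maintained | 4 | 4 | 4/10 to 4/6 = 0.40 to 0.67 | 0.00 |
| (b) half lost | 4 | 2 | 2/10 to 2/6 = 0.20 to 0.33 | −2/12 to −2/8 = −0.17 to −0.25 |
| (c) all lost | 4 | 0 | 0.00 | −4/12 to −4/8 = −0.33 to −0.50 |

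**3. Sampling scatter.** Assume 30 per arm, SD_pre 8, SD_post = SD_FU = 10, correlations pre-post 0.5, post-FU 0.7 and pre-FU 0.5, complete data, and change scores in place of the multilevel model.

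- Variance of change, post to follow-up: 100 + 100 − 2·0.7·100 = 60. SE of the difference: √(60·2/30) = 2.00 points, or 0.20 in d.
- Variance of change, pre to follow-up: 64 + 100 − 2·0.5·80 = 84. SE: √(84·2/30) = 2.37 points, or 0.30 in d.
- Case (b): the planned d is negative with probability Φ(2/2.00) = 0.84, the from-baseline d with probability Φ(−2/2.37) = 0.20.

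Simulation of 20,000 trials agrees. In case (a) the planned d averages 0.00 and the from-baseline d 0.51.

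**4. Coverage by the binary tests.** Case (a), with the inputs of step 3. Further assumptions: pre-treatment mean 68 and a 10-point improvement in the lagging arm. Recovery is an improvement of at least 7 points with a follow-up score at or below the cut-off.

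| Comparison at follow-up | Power |
|---|---|
| Continuous, from baseline | 0.38 to 0.39 |
| Recovery, cut-off 53 (Fisher) | 0.16 |
| Recovery, cut-off 47 (Fisher) | 0.10 |
| Reliable improvement, assumed reliability 0.80 to 0.95 | 0.14 to 0.19 |

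Over 15 to 60 per arm and SD_post 8 to 12, power runs from 0.17 to 0.78 for the continuous contrast, 0.04 to 0.52 for recovery at 53 and 0.04 to 0.31 at 47.

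**5. Rebuilding the effect from the reported segments.** Adding the two d values fails when the SDs differ. In case (c) with SDs 8 and 10, 4/8 − 4/10 = 0.10, while the from-baseline d is 0. With both SDs reported, (d_post·SD_pre + d_FU·SD_post)/SD_pre recovers the point estimate. Its SE needs the covariance between segments. With the inputs of step 3:

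- Variance of change, pre to post: 64 + 100 − 2·0.5·80 = 84.
- Covariance of the segments: 70 − 100 − 40 + 40 = −30.
- SE assuming independence, relative to the correct one: √((84 + 60)/(84 + 60 − 60)) = 1.31.

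Over 54 assumed settings (SD_pre 8, SD_post 8 to 12, correlations pre-post 0.3 to 0.7, post-FU 0.6 to 0.8, pre-FU 0.3 to 0.5) the segment correlation runs from −0.58 to 0.41. The SE ratio runs from 0.85 to 1.54, with a median of about 1.19.

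**The case against.** The strongest reply is that nothing is hidden or miscalculated. The plan names the segment twice. The quantity is a valid randomised contrast of change after treatment, and such a contrast should be 0 under full maintenance and negative when an advantage shrinks. On this view the cases above only show that two estimands differ. **This stands as far as it goes:** there is no bias and no false-positive risk, and the choice of SD is a stated convention. It does not supply the missing estimand, and it does not make a change score an effect at follow-up.

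A second reply is that little is lost. The point estimate can be rebuilt, and an interval that assumes independence would usually be somewhat too wide. Under the inputs of step 3, a from-baseline d of 0.50 has a 95% half-width of 1.96 × 0.296 = 0.58, so it would be inconclusive anyway. Efficacy is secondary. **This limits the weight.** But an imprecise estimate with its correct interval is what a pilot should report, and readers cannot obtain that interval from the segment results.

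Third, the plan retains the time-by-group term only if the likelihood ratio test favours it, whereas the simulation always estimates it. The 84% is therefore a property of the contrast and not a forecast of what would be reported. **This stands.** The algebra does not depend on it.

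**Conclusion.** The concern holds and should be fixed. The d described as a follow-up effect is differential change after post-treatment, and no continuous between-group effect from pre-treatment to follow-up is planned for any outcome. That conclusion, the zero under full maintenance and the sign reversal under partial loss follow from the text and algebra alone. The numerical size rests wholly on assumed inputs. The binary PSWQ comparisons fill the gap only in part and, under those inputs, with less power. The consequence is confined to a secondary question of a pilot.

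**What to change.** Define the follow-up effect as the model-based between-condition difference in change from pre-treatment to follow-up, divided by the pooled pre-treatment SD, with a 95% CI. Obtain it from one model containing all assessments: either categorical time, or piecewise slopes with the two segment contrasts summed. Keep the present quantity but call it differential change from post-treatment to follow-up, preferably on the same pre-treatment SD so that all the d values share one scale.

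The cost is small. The plan does not say whether the two segments form one model or two. If one piecewise model, only a summed contrast is added; if two, a joint model must be specified and fitted. SAP wording changes, no new data are needed, and no planned analysis is lost.
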